- 14 SAEs occurring after signing of the informed consent form (ICF) will be recorded and reported to the sponsor or designee by the investigator within 24 hours of becoming aware of the SAE.

Table 3 Schedule of Assessments: Cohorts 3, 4, and 6

Study Visit	V00	V01	V02	V03	V04	V05	V06	V07	V08	V09	V10	V11	V12	V13	Unsch Visit	Early Term Visit
Study Day(s)	SCR -30 to -1	Day 1	Day 2 +1d	Day 4 +2d	Day 8 +2d	Day 15 ±2d	Day 29 ±3d	Day 30 +1d	Day 32 +2d	Day 37 +2d	Day 58 ±3d	Day 86 ±3d	Day 209 ±3d	Day 394 ¹⁶ ±7d		
Vaccination		X					X									
45 Minute Evaluation After Study Vaccination		X					X									
Distribute Memory Aid and Study-Related Materials		X					X									
Review Memory Aid			X	X	X			X	X	X					X ⁴	X ⁴
Adverse Events		X	X	X	X	X	X	X	X	X	X				X ⁵	X ⁵
SAEs/AESIs Including PIMMCs/MAAEs/NOCMCs ¹³	X ¹⁴	X	X	X	X	X	X	X	X	X	X	X	X	X	X	X
Phone Visit ⁶			X	X				X	X							
Saliva Collection for Antibodies		X			X	X	X			X			X			

Abbreviations: AESI, adverse event of special interest; BP, blood pressure; ECG, electrocardiogram; HBsAg, hepatitis B surface antigen; HCV, hepatitis C virus; HIV, human immunodeficiency virus; MAAE, Medically Attended Adverse Event; NOCMC, New Onset Chronic Medical Condition; SAE, serious adverse event; PCR, polymerase chain reaction; PIMMC, Potentially Immune-Mediated Medical Condition; SARS-CoV-2, severe acute respiratory syndrome coronavirus 2; SCR, screening; Unsch, unscheduled

1 Includes white blood cells (WBCs), hemoglobin (Hb), platelets (PLT), alanine aminotransferase (ALT), aspartate aminotransferase (AST), alkaline phosphatase (ALP), total bilirubin, creatine kinase (CK), serum creatinine, prothrombin time (PT)/international normalized ratio (INR), and activated partial thromboplastin time (aPTT)

2 Includes WBC, Hb, PLT, ALT, AST, ALP, total bilirubin, CK, and creatinine

3 Includes SARS-CoV-2 serology (N-specific) only

4 If within 7 days after each vaccination (prime or boost dose)

5 If prior to Visit 10

6 Can be phone, text, or e-mail contact

7 A nasal swab for SARS-CoV-2 should be performed within 3 days of COVID-19 symptoms and repeated after 7 days.

8 ECG data will include heart rate and RR, PR, QT, and QRS durations.

9 ECG will be performed up to 72 hours before the 1st and up to 72 hours before the 2nd study vaccinations.

10 Cardiac biomarker assessments will include troponin T, C-reactive protein (CRP), and erythrocyte sedimentation rate (ESR).

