
Risks to subjects receiving the study products are expected to primarily involve mild to moderate local reactions, which have been observed in animal studies and are generally observed and expected for other IM-administered vaccines. These local reactions may consist of transient and dose-dependent pain, swelling, and erythema. Possible systemic reactions, which are also transient, may include fever, fatigue, chills, headache, myalgia, and arthralgia. In addition, other AEs that have been generally associated with approved IM administered vaccines have included mild hematological and clinical chemistry abnormalities, which are usually reversible.

The investigational vaccines should not be administered to individuals with a known hypersensitivity to any component of the study product. There is also a potential risk of hypersensitivity reactions following the administration of any study product.

Several animal studies with experimental whole-virus inactivated and subunit vaccines of other coronaviruses have shown enhanced immunopathology in a greater number of vaccinated animals compared to controls upon subsequent virus infection. These experimental vaccines often exhibited Th2-biased immune responses or elicited antibodies that had poor neutralizing activity against the virus. In preclinical studies of Gritstone's SAM, a predominant Th1-focused immune response was observed.

The relevance of these observations in humans is unknown. Notably, most people during their lifetimes have likely been infected with one or more of the 4 endemic strains of human coronaviruses (hCoV 229E, NL63, OC43, and HKU1) that circulate globally and are responsible for 10-30% of mild to moderate upper respiratory tract infections. Despite the likelihood of cross-reactive antibody responses with poor functional activity, no evidence of enhanced CoV disease in humans has ever been reported.

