12 STATISTICAL CONSIDERATIONS

12.1 Study Hypotheses

This is a Phase 1, multi-center, open-label study of GRT-R910 used as a boost vaccine following prior vaccination with a first-generation vaccine, and it is not designed to formally test a specific hypothesis. The study aim is to characterize and obtain preliminary estimates of the safety, reactogenicity, and immunogenicity of different doses of the GRT-R910 vaccine in healthy adults 18 years and older. No hypothesis testing comparing the different vaccine schedule and cohorts will be performed.

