4.2. Key definitions and principles

The following principles and definitions will be applied to all tables, listings, and figures (TLFs), unless otherwise specified, are described in [Table 2](#).

Table 2 Principles and definitions for all tables, listings, and figures

Principle/definition	Value
Baseline	
Is defined as the last available valid, non-missing observation for each subject on or before the vaccination of the prime dose at V01/Day 1. Repeat and unscheduled assessments will be included in the derivation of the baseline values.

Change from Baseline	
Is defined as difference between the results collected/derived at a post-baseline visit and baseline value.
 
The change from baseline value at each post-baseline visit will be calculated for continuous parameters using the following formula:
 $\text{Change from baseline} = (\text{Result at post-baseline visit}) - (\text{Baseline value})$ 
The change from baseline value will only be calculated if the specific post-baseline visit/time point result and the baseline value for the parameter are both available and will be treated as missing otherwise. In the data listings, the change values will be set to 'N/A' (not applicable) for pre-baseline assessments.

Study Day	
Is defined as the relative day of the event starting with the date of vaccination of the prime dose (the reference day) as Day 1 (there will be no Day 0).
 
The study day of events occurring before the vaccination of the prime dose will be calculated in the following way:
 $\text{Study day (before vaccination)} = (\text{Date of event}) - (\text{Date of Vaccination of Prime Dose})$ 
For events occurring on or after the vaccination will be calculated as:
 $\text{Study day (after vaccination)} = (\text{Date of event}) - (\text{Date of Vaccination of Prime Dose}) + 1$ 
Study days will only be calculated for events with complete dates and will be undefined for events that are 'Ongoing' at the end of the study.

Display Convention of Results	
Results will be center-aligned in all summary tables and left-aligned in all listings. Subject identifiers, visits, parameter labels, and comments may be left-aligned if required.

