9.6. Electrocardiogram

Electrocardiogram (ECG) will be performed for Cohort 1 and 2 receiving booster dose only and Cohort 3, 4, and 6.

The ECG data will include heart rate and RR, PR, QT, and QRS durations. The investigator will be responsible for providing the interpretation of clinical significance for all ECG results.

The ECG assessments will be summarized as mean, SD, median, min, max, and mean of actual value and as mean, SD, median, min, and max of change from baseline. An interpretation by study days table in ECG will be summarized for the SAF

For subject with Early Termination (ET) visit, the ET visit will be set to the next protocol scheduled visit following ET within the specific study period. If the subjects completed all the scheduled visits and then discontinued, no mapping will be done.

All the ECG data will be listed.

10. Interim Analysis

No interim analysis was planned for this study; however, there may be unplanned interim analyses in light of the nature of Phase 1 study.

11. Changes in the Planned Analysis

- Efficacy analysis was added to the section 8.1
- Explained the occurrence of potential unplanned interim analyses in section 10.
- Calculation of solicited AE duration in section 9.1.2

12. References

1. ICH. Guidance for Industry (E9 Statistical Principles for Clinical Trials)
2. Gritstone bio, Inc. Clinical study protocol GO-009 Version 5.0 09 Feb 2023.
3. https://www.sas.com/en_us/home.html
4. Martin Bland Prof. of Health Statistics University of York, Detecting a single event

Gritstone bio, Inc.
GO-009

Statistical Analysis Plan, Version 5.0
Date Issued: 09UN2023

5. ICH. Guidance for Industry (Integrated Addendum to ICH E6(R1): Guideline for Good Clinical Practice E6(R2))
6. Clopper, C.J., and Pearson, E.S. (1934), "The Use of Confidence or Fiducial Limits Illustrated in the Case of the Binomial", *Biometrika* 26, 404-413
7. U.S. Department of Health and Human Services Food and Drug Administration Center for Biologics Evaluation and Research, "Toxicity Grading Scale for Healthy Adult and Adolescent Volunteers Enrolled in Preventive Vaccine Clinical Trials", 2007

Approved

Gritstone bio, Inc.
GO-009

Statistical Analysis Plan, Version 5.0
Date Issued: 09JUN2023

13. Appendices

Appendix 1

Table 6 Schedule of Study Procedures: Cohorts 1 and 2 – Subjects NOT receiving booster dose

Study Visit	V00	V01	V02	V03	V04	V05	V06	V07	V08	Unsch Visit	Early Term Visit

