79	Table	14.3.5.4.3	Summary of Actual Value and Change from Baseline in Cardiac biomarker assessments	Safety Analysis Set – Cohort 1 and 2 with Booster Dose
80	Table	14.3.5.4.4	Summary of Actual Value and Change from Baseline in Cardiac biomarker assessments	Safety Analysis Set – Cohort 3, 4, and 6
81	Table	14.3.5.5.1	Screening Physical Examination Results	Safety Analysis Set
82	Table	14.3.5.6.1	Electrocardiogram Interpretation by Visit	Safety Analysis Set – Cohort 1 and 2 with Booster Dose
83	Table	14.3.5.6.2	Electrocardiogram Interpretation by Visit	Safety Analysis Set – Cohort 3, 4, and 6
84	Table	14.3.5.6.3	Change from Baseline in Electrocardiogram Results	Safety Analysis Set – Cohort 1 and 2 with Booster Dose
85	Table	14.3.5.6.4	Change from Baseline in Electrocardiogram Results	Safety Analysis Set – Cohort 3, 4, and 6
86	Table	14.4.1	Vaccination Administration	Safety Analysis Set
87	Table	14.4.2.1	Recent Vaccinations and Concomitant Medications	Safety Analysis Set
88	Listing	16.2.1.1	Screen Failures	All Screened Subjects Analysis Set
89	Listing	16.2.1.2	Subject Disposition	Intent-to-Treat Analysis Set*
90	Listing	16.2.2.1	Inclusion/Exclusion Criteria	All Screened Subjects Analysis Set
91	Listing	16.2.2.2	Protocol Deviations	Intent-to-Treat Analysis Set*
92	Listing	16.2.3	Analysis Sets	All Screened Subjects Analysis Set
93	Listing	16.2.4.1	Demographics	Safety Analysis Set
94	Listing	16.2.4.2	SARS-CoV-2 PCR	Safety Analysis Set
95	Listing	16.2.4.3	Medical or Surgical History	Safety Analysis Set
96	Listing	16.2.4.4	Recent Vaccinations or Concomitant Medications	Safety Analysis Set
97	Listing	16.2.5.1	Vaccination	Safety Analysis Set
98	Listing	16.2.7.1	Solicited Local Adverse Events	Safety Analysis Set
99	Listing	16.2.7.2	Solicited Systemic Adverse Events	Safety Analysis Set

Gritstone bio, Inc.
GO-009

Statistical Analysis Plan, Version 5.0
Date Issued: 09JUN2023

100	Listing	16.2.7.3	Unsolicited TEAEs	Safety Analysis Set
101	Listing	16.2.7.4	Treatment-Related Unsolicited TEAEs	Safety Analysis Set
102	Listing	16.2.7.5	Serious TEAEs	Safety Analysis Set
103	Listing	16.2.7.6	Serious Treatment-Related TEAEs	Safety Analysis Set
104	Listing	16.2.7.7	Unsolicited TEAEs Leading to Vaccine Dose Delay	Safety Analysis Set
105	Listing	16.2.7.8	Unsolicited TEAEs Leading to Study Discontinuation	Safety Analysis Set
106	Listing	16.2.7.9	Unsolicited TEAEs Leading to Study Drug Discontinuation	Safety Analysis Set
107	Listing	16.2.7.10	Fatal TEAEs	Safety Analysis Set

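### SAP 9.6 tabulates change in QT without heart-rate correction although RR is recorded at the same ECG; a derived QTcF would make the tables readable at no data cost

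*SAP*

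**What the plan says.** SAP 9.6 covers the boosted subjects of Cohorts 1 and 2 and all of Cohorts 3, 4 and 6. It lists the measurements: "The ECG data will include heart rate and RR, PR, QT, and QRS durations". Protocol 10.1 has the same list, as do the ECG footnotes to the schedules in Protocol 3.2 ("ECG data will include heart rate and RR, PR, QT, and QRS durations") and in SAP Appendix 1.

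On analysis, SAP 9.6 says "The ECG assessments will be summarized as mean, SD, median, min, max, and mean of actual value", with a matching set of statistics for change from baseline. SAP 4.2 defines that change plainly: it "Is defined as difference between the results collected/derived at a post-baseline visit and baseline value". SAP Appendix 2, Table 9 carries this into Tables 14.3.5.6.3 and 14.3.5.6.4, titled "Change from Baseline in Electrocardiogram Results". Tables 14.3.5.6.1 and 14.3.5.6.2 give the ECG interpretation by visit, for which SAP 9.6 says "The investigator will be responsible for providing the interpretation of clinical significance for all ECG results". All ECG data are also to be listed.

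No section of either document mentions QTc, a correction formula, a QT criterion, or an analysis of QT conditional on RR. SAP section 9 counts ECGs among the assessments used to judge safety.

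**The concern.** The QT interval shortens as heart rate rises and lengthens as it falls. If QT is the only repolarisation measure tabulated, its change from baseline contains two components: any change in repolarisation, and whatever the pulse did between the two tracings. The second can imitate the first or hide it.

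The vaccine need not act on heart rate for this to happen. Resting pulse varies from visit to visit, and each subject's raw QT change carries that variation. The SD, minimum and maximum of change are the most exposed, because they reflect individual differences that do not average out.

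What is at stake is how readable one set of safety tables is. RR, the quantity needed to remove the pulse component, is already collected at the same ECG.

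**Working it through.** **The plan's own figure.** Neither document states a QT value, a heart-rate value or an expected ECG change, so there is nothing to reproduce.

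**When the ECGs are taken** (Protocol Table 2; SAP Tables 7 and 8 with footnotes).
- Boosted Cohorts 1 and 2: pre-dose on Days 1 and 113; after the doses on Days 8, 29, 57, 120, 142, 170, 293 and 478.
- Cohorts 3, 4 and 6: pre-dose on Days 1 and 29; after the doses on Days 8, 37, 58, 86 and 209, plus Day 394 for those in Cohorts 3 and 4 who reach it.
- First ECG after each dose: 8 - 1 = 7 days and 120 - 113 = 7 days in the first group; 8 - 1 = 7 days and 37 - 29 = 8 days in the second. Visit windows at these points run later only, and visits move with the actual date of the second dose.

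**Assumed inputs (not in the documents).** QTcF 410 ms, baseline pulse 65 bpm, pulse changes from -5 to +10 bpm.

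**Formula.** With RR = 60/HR seconds, Fridericia's correction gives QT = QTcF × (60/HR)^(1/3). Baseline: 410 × (60/65)^(1/3) = 399.2 ms.

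| Later pulse (bpm) | QTcF (ms) | Raw QT (ms) | Change in raw QT (ms) | Change in QTcF (ms) |
|---|---|---|---|---|
| 65 | 410 | 399.2 | 0.0 | 0 |
| 70 | 410 | 389.5 | -9.7 | 0 |
| 75 | 410 | 380.6 | -18.6 | 0 |
| 60 | 410 | 410.0 | +10.8 | 0 |
| 75 | 430 | 399.2 | 0.0 | +20 |

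The first four rows have no repolarisation effect, yet raw QT moves whenever the pulse does. In the last row a 20 ms rise in QTcF is cancelled by a 10 bpm faster pulse.

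**Sensitivity.** For QTc of 400 to 420 ms and a baseline of 60 to 70 bpm, with QTc held constant:
- +5 bpm: raw QT changes by about -9 to -11 ms under Fridericia, or -13 to -17 ms under Bazett (square root in place of cube root).
- +10 bpm: about -17 to -21 ms, or -24 to -31 ms.
- -10 bpm: about +20 to +26 ms, or +30 to +40 ms.

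The direction does not depend on the formula; the size does.

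**Spread.** Near 65 bpm the slope is QT/(3 × HR) = 399.2/195 = 2.05 ms per bpm. If the within-subject change in pulse had an SD of 5 to 10 bpm (assumed), pulse alone would contribute an SD of 2.05 × 5 = 10.2 ms to 2.05 × 10 = 20.5 ms to raw QT change. In a cohort of 10 that is a standard error of 10.2/√10 = 3.2 ms to 20.5/√10 = 6.5 ms.

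**The case against.** **Timing.** A reader might infer that a reactogenic vaccine will drive the pulse up and distort QT by tens of milliseconds. With constant QTcF of 410 ms, for instance, a rise from 60 to 80 bpm takes raw QT from 410.0 to 372.5 ms, a change of -37.5 ms. The documents do not support that expectation. Protocol 4.3.3 says "Possible systemic reactions, which are also transient, may include fever, fatigue, chills, headache, myalgia, and arthralgia", and places flu-like symptoms within the first day in cancer patients given the same platform. No ECG is scheduled in that period. This part of the objection stands; what remains is ordinary pulse variation.

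**The data allow separation.** A reader might also infer that a repolarisation effect and a pulse effect could never be told apart. That goes too far. Heart rate and RR are among the summarised ECG data, every ECG is listed, and anyone with the listings can compute QTc. However, separate summaries of QT and RR do not pair the two within a subject, so the planned tables do not themselves do it. Under SAP section 4, an analysis added later would be labelled exploratory and post hoc.

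**Investigators read every ECG.** This is a real safeguard for individual tracings. It comes with no stated QT criterion, and it does not make the cohort table of QT change easier to interpret.

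**Nothing depends on QT.** ECG is not a primary or secondary outcome. Protocol 12.1 states that "No hypothesis testing comparing the different vaccine schedule and cohorts will be performed". The cardiac risk named in Protocol 10.2.1, as the reason for the biomarkers, is myocarditis. No halting rule refers to QT, and cohorts of 10 without a control would give only descriptive QTcF results too. All of this stands and sets the weight of the point.

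**Conclusion.** The point holds as a minor one. The only QT change the SAP will tabulate is uncorrected, so its mean, SD, minimum and maximum mix repolarisation with pulse change between visits. Under the assumptions above, a pulse change of 5 to 10 bpm moves raw QT by roughly 10 to 20 ms with no repolarisation effect, and can cancel a QTcF change of similar size. With no pulse change the distortion is zero. The true size in this trial cannot be known from the documents.

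It would be wrong to conclude that the trial's safety findings are unsound or that a QT signal is expected to be missed. The documents raise no repolarisation concern, no endpoint or decision rests on QT, and the underlying data are fully reported. The claim is only that the planned tables use a less interpretable measure when a better one can be derived from what is already collected.

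**What to change.** In SAP 9.6, pre-specify that QTcF = QT / RR^(1/3) is derived for every ECG, using QT and RR from the same tracing with RR in seconds. Report its actual value and change from baseline beside raw QT in Tables 14.3.5.6.3 and 14.3.5.6.4.

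The SAP 4.2 definition of change already covers derived results, so it needs no edit. Naming one formula in advance also avoids a choice between corrections after the data are seen.

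The cost is one derived variable and added rows in two tables. It needs no new data, visit or procedure, and does not touch clinical management.
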